#### **c. Potential Risks.**

- Vascular measures (brachial artery FMD, carotid artery compliance and pulse wave velocity). There are no known risks to participants associated with these procedures. Some participants may have discomfort in the hand (pins and needles) during the cuff occlusion portion of the FMD measurement.
- Functional magnetic resonance imaging (fMRI) measurements. The magnetic field of the MR environment has the potential to cause burns or bodily injury if ferrous metal objects are implanted in the body, or if personal articles containing ferrous material are brought into the environment. The risk of MRI to pregnant women and fetuses is currently unknown. The MRI may cause discomfort due to scanner noise. There may be some discomfort from lying still and in one position for a long time. At sufficient exposure levels, peripheral nerve stimulation is perceptible as "tingling" or "tapping" sensations. PNS symptoms will usually subside shortly after the scan is completed. Participants may feel nervousness or feelings of claustrophobia. There is a risk that the image will reveal an observation concerning an individual research participant that has potential clinical importance but is beyond the aims of this protocol. In the event of the confirmation of a significant anomaly in a participant's brain image, this information will likely be distressing to the participant.
- Cognitive testing. Subjects may experience frustration or anxiety during the testing session. It is possible that this testing could reveal previously unrecognized significant cognitive impairment that could be distressing to the subject.
- Study drugs. As participants in the FAME study, all participants in this proposed research will be randomized to receive placebo (saline) or GnRHa (leuprolide acetate) 3.75 mg/mo by intramuscular injection every month for 6 months (6 doses), plus or minus exercise. Women randomized to GnRHa and no exercise will receive 3 additional monthly doses after completion of the FAME study, for a total of 9 doses. During these 3 additional months, these women will also receive weekly transdermal 17 $\beta$ -estradiol 0.075 mg/d (12 doses), and oral medroxyprogesterone acetate 5mg/day for 12 days (12 doses) at the beginning of week 6 of estradiol therapy to minimize breakthrough bleeding and thereby enhance

participant retention.

#### Leuprolide acetate

Contraindications for use include: hypersensitivity to GnRH, GnRH agonist analogs or any of the excipients in Lupron Depot; undiagnosed vaginal bleeding; known or suspected pregnancy; lactation.

In women who are pregnant, use of leuprolide acetate may cause fetal abnormalities.

Leuprolide acetate may cause an anaphylactic reaction in volunteers with hypersensitivity to GnRH.

Regular menstruation should stop during leuprolide acetate therapy but spotting or breakthrough bleeding may occur. Cessation of menses does not ensure that pregnancy will not occur. Normal menstrual function is usually restored within 2-3 months after therapy is discontinued.

Leuprolide acetate may cause symptoms related to hypoestrogenism including hot flashes, headaches, nausea, emotional lability, decreased libido, acne, myalgia, sleep disorder, reduction in breast size, and vaginal dryness. Bone loss may occur, although the amount lost over the 24-week intervention should not be clinically significant and should be recovered slowly after discontinuation of leuprolide acetate treatment. There may be a development or worsening of depression and the occurrence of memory disorders.

Leuprolide acetate therapy for 24 weeks may cause an increase in fat mass (1-2 kg), a decrease in fat-free mass (1-1.5 kg), an increase in total, LDL, and HDL cholesterol (5-10%), and an increase in triglycerides (15-20%).

Local injection site reactions including induration and abscess may occur.

#### Transdermal 17 $\beta$ -estradiol

Contraindications to use include: hypersensitivity to estradiol or any of the components in the transdermal formulation; arterial thromboembolic disease; breast cancer; deep vein thrombosis; pulmonary embolism; estrogen-dependent neoplasia; undiagnosed vaginal bleeding; liver disease; pregnancy; or thrombophilic disorder. Transdermal estradiol may cause irritation at the application site, edema, fluid retention and weight gain, bloating, nausea, vomiting, headache, depression, breast tenderness and withdrawal bleeding. Rare but serious side effects include heart disease, myocardial infarction, breast cancer, hypercalcemia, gallbladder disease, venous thromboembolism, anaphylaxis, stroke, endometrial cancer, ovarian cancer, pulmonary embolism and breast cancer.

#### Medroxyprogesterone acetate

Contraindications to use include: hypersensitivity to progesterone or any of the ingredients, breast cancer, liver disease, estrogen or progesterone-dependent neoplasia, pregnancy, thromboembolic disorders, cerebral vascular disease, and undiagnosed vaginal bleeding. Oral progesterone may cause weight gain, abdominal pain, dizziness, headache, nervousness, amenorrhea, menstrual spotting, reduced libido and fatigue. Rare but serious side effects include anaphylaxis, decreased bone mineral density and fracture of bone.

- Venipuncture. There is a small risk of local hematoma, infection, and thrombosis associated with intravenous blood sampling.
- Confidentiality and privacy. The use of questionnaires, interviews, and collection of personal medical information poses a risk to confidentiality and privacy and may cause embarrassment.

## **2. Adequacy of Protection Against Risks**

### **a. Recruitment and Informed Consent.**

Subjects will be recruited from the FAME study. After volunteers complete screening and are determined to be eligible for the FAME study, they will be invited to participate in this sub-study. Interested participants will meet individually with a member of the research team to review all aspects of the study and consent form in a private, quiet environment. Volunteers will be encouraged to ask any questions they may have regarding the study and what is expected of them should they choose to participate. A description of the MRI procedures is included in the consent form, and all participants will be given a verbal description of the MRI screening process and potential risks of MRI studies. The member of the study team obtaining consent will stress that: 1) all research participation is voluntary, 2) subjects may withdraw at any time, and 3) the decision to participate or not participate will not affect the subject's medical care or any benefits to which the subject is entitled. They will further be asked to explain the consent form in their own words to ensure understanding of the study and what is expected of them. The consent form details the experimental protocol and potential risks, and must be signed prior to any participation in the study. The protocol and consent forms will be approved by the Colorado Multiple Institution Review Board (COMIRB) and the CTRC. The CTSA at the University of Colorado AMC has a designated officer for review of human subjects protections for research utilizing CTSA resources. Each volunteer will be given a copy of the signed consent form; the original will be kept in the subject's study file. In compliance with HIPAA, each participant will sign the institutional COMIRB/HIPAA form: Authorization to Use or Release Health Information for Research Purposes. This form describes all information that will be obtained

for research purposes, and who will have access to this information. All subjects must have the capacity to understand the nature of the study and potential risks involved in the study. The purpose and procedures for each study test will be reviewed with the subject prior to its administration to ensure subjects understand what is being asked of them, and agree to proceed.

b. Protections Against Risks.

- Vascular measurements (brachial artery FMD, carotid artery compliance, and pulse wave velocity). There are no known risks to participants associated with these procedures. If a participant has significant discomfort or pain with the cuff occlusion for the FMD measurement, the procedure will be stopped.
- fMRI measurements. This protocol will be performed using an MR scanner employing pulse sequences and hardware that have been approved by the FDA for human clinical use. The field strength is 3 Tesla and all relevant operating characteristics (RF power deposition, rate of change of the field gradients, coil design) fall within the limits of FDA guidelines for NMR exposure. Participants will be carefully screened to exclude those who may have metal in or on their bodies that cannot be removed (e.g., bullets, metal filings, body piercings, etc.). MR Facility rules strictly forbid staff from entering the magnet room carrying metal objects. The risk of claustrophobia is minimized by screening subjects for self-reported claustrophobia and making sure the subject is lying comfortably with head and neck supported and providing ear protection with headphones, a mirror to see out, a button to signal distress, and an intercom. Scan time will be kept to a minimum. If they are unsure about whether or not they may be pregnant, female participants will be given the opportunity to complete a urine pregnancy test immediately before the scanning period, and those with a positive result will not be scanned. With regard to PNS, participants are given a squeeze ball to use in case of an emergency. They are informed that if they experience PNS related sensations or are otherwise uncomfortable, they can alert the MRI technologist via the squeeze ball and the technologist will stop the scan immediately.

In the case of an anomalous finding in a brain image, the following procedure is followed:

1. The technologist and/or research personnel flag potential abnormalities.
2. The MRI technologist notifies the INC Director of Operations, the MRN Director of Research and Clinical Operations, and the P.I.
3. The scan gets queued to the radiologist worklist in COINS. All cases of suspected incidental findings are sent for formal neuroradiologic review at MRN.
4. The radiology review contains a written summary of the findings and classifies the referral status into one of these categories:
  - There is not enough information from the MRI scan to complete a full review. No obvious abnormalities found.
  - MRI shows nothing obvious that needs medical attention.
  - MRI shows something that may or may not be of medical concern. Participants should consider discussing the enclosed report with their doctor.
  - MRI shows something that needs to be brought to the attention of your doctor. Participants may also be contacted by the study team and/or MRN Medical Director about this report.
5. The PI will get an electronic copy of the radiology review (coded via URSI) as soon as the review is completed. If an urgent referral is recommended, the PI should discuss the review with the Medical Director prior to contacting the participant.
6. If a referral is recommended, the PI will contact the participant and explain that an unusual feature was observed in their scan. The PI provides the contact information for the Medical Director who reviewed the image (this information is in the letter mailed to the participant as well). Routine referrals are handled on a case by case basis and up to the PI/Medical Director to determine if the participant should receive a call in advance.
7. All cases reviewed will generate a formal radiology report, which is printed on letterhead and a copy of which is mailed to the participant. In the case of an urgent referral, someone from the study team or the Medical Director will contact the participant prior to the letter being mailed.

- Cognitive testing. Testing will be conducted in a dedicated, private, quiet room by an experienced psychometrician. Any subject who expresses distress or discomfort with the testing may elect to take a break, or stop the testing. Subjects meeting pre-specified cut-points on any of the cognitive tests that may indicate clinically significant cognitive impairment will be flagged for review by [name]. [name] would discuss the results with the volunteer and her health care provider to ensure appropriate follow up and clinical evaluation. We have obtained a Certificate of Confidentiality from the NIH to provide an additional level of protection for the cognitive tests.

- Study drugs. The risks associated with use of the study drugs will be minimized by enrolling participants who do not have contraindications for their use. All participants will have been screened for contraindications to GnRHa through the FAME study. Participants will be observed for 30 min after drug injection to monitor for new hypersensitivity reactions. Absence of pregnancy will be confirmed before injections are administered. Women will be instructed that they should not become pregnant while taking study drugs because of risks to the fetus. They will be instructed that cessation of menses may or may not occur during the study and that cessation of menses does not provide protection against pregnancy; contraception (not hormonal) must be used.
- Venipuncture. The risks of hematoma and infection are minimized by having trained personnel perform the procedures using sterile techniques.
- Confidentiality and privacy. These risks will be minimized by not including personal identifying information on the forms, when possible, and by conducting interviews and collection of personal information in a private setting.

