### 3.b. Methods

**Subjects.** Volunteers will be participants who have been recruited, screened and randomized to participation in the FAME study. Women will be nearing menopause (40-60 yrs) with normal menstrual cycles. Subjects will have had a medical history, physical examination, depression assessment, and clinical laboratory evaluation (complete blood count, comprehensive metabolic panel and TSH). Participants will be excluded from FAME for the following: irregular menstrual cycles, serum FSH>25mIU/mL measured during the first 5 days of the menstrual cycle, pregnant or lactating, on hormonal therapy, known hypersensitivity to leuprolide, score of  $\geq 18$  on the Beck Depression Inventory, proximal femur or lumbar spine T-score  $<-2.0$ , abnormal vaginal bleeding, thyroid dysfunction, uncontrolled hypertension ( $>150/90$ ), currently exercising  $\geq 30$  min/d  $>4$  d/wk or BMI $\geq 35$ kg/m^2. Eligible FAME volunteers will be randomized to receive monthly injections of placebo (saline) or GnRHa (leuprolide acetate, 3.75 mg) for 6 mos. GnRHa-treated women are further randomized to endurance exercise training, or no exercise. Prior to beginning the intervention treatment for FAME, volunteers will also be invited to participate in this study of vascular mechanisms for the cognitive effects of ovarian suppression. Participants will be excluded for: Mini Mental State Examination score  $\leq 27$ , history of neurologic disease or major psychiatric illness, major depressive episode within the past 12 months, history of learning disability, or < high-school education. In order to protect the health and safety of the participants, exclusion criteria for this study will include any contraindication to magnetic resonance scanning (e.g., metal in body, claustrophobia, pregnant). These exclusions are specific to MRI and are consistent with most studies involving MRI. Potential participants will be screened for the presence of any of these exclusion criteria prior to participating in this MRI study.

Volunteers will undergo vascular and cognitive/fMRI testing at baseline and 6 months, corresponding to the beginning and end of the FAME study. Baseline testing will be performed during the early follicular phase (i.e., days 2-6) of the menstrual cycle.

[figure not shown]

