Separate from the parent FAME study, women randomized to GnRHa and no exercise will complete an additional 3 months of GnRHa + transdermal E2 add-back, with vascular and cognitive/fMRI testing at 9 months (Fig 2).

**Sub-study.** An additional group of up to 30 late-perimenopausal or postmenopausal women who have had carotid artery compliance and brachial artery FMD performed within the last 6 months will also be enrolled. There is no intervention performed in this group, rather, they will serve as a comparison to the other premenopausal intervention groups. Similar to premenopausal women, late perimenopausal and postmenopausal women will be excluded for: Mini Mental State Examination score  $\leq 27$ , history of neurologic disease or major psychiatric illness, major depressive episode within the past 12 months, history of learning disability, < high-school education, or contraindications to MRI. Experimental procedures in this group of participants will be limited to cognitive testing, fMRI and apolipoprotein ε4 genotyping.

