### Experimental procedures

**Drug intervention.** Volunteers will receive monthly intramuscular injections of placebo (saline) or leuprolide acetate (3.75mg depot suspension; Abbott Laboratories; Abbott Park, IL) for 6 mo. A subset (N=10) of women receiving GnRHa will continue for an additional 3 mo. Absence of pregnancy will be confirmed before each dose. A single injection of leuprolide produces an initial stimulation (~2 wk) followed by a prolonged

Figure 2. Study design.

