suppression of pituitary gonadotropins and ovarian hormone secretion; repeated monthly dosing maintains suppression of ovarian function. Leuprolide has been used clinically for up to 1 yr without serious adverse events, although there may be a decrease in bone mineral density that recovers slowly following cessation of treatment. Side effects are those typical of E2 deficiency including hot flashes, headaches, nausea, emotional lability, decreased libido, acne, myalgias, sleep disorder, reduction in breast size, and vaginal dryness. There may be a development or worsening of depression and the occurrence of memory disorders. In studies of women with uterine fibroids, GnRHa 3.75 mg/mo induced amenorrhea in 61%, 86%, and 90% of women after 1, 2, and 3 mo of treatment, respectively. Return of menses typically occurred within 2-3 mo of cessation of therapy. Injections will be administered in a blinded manner, but participants on GnRHa may know their assignment because of the induction of amenorrhea and menopausal symptoms. Subjects will be instructed not to discuss their assignment with the outcome assessors. Subjects receiving an additional 3 mos of GnRHa in this sub-study will also receive weekly transdermal 17 $\beta$ -E2 add-back therapy (0.075 mg/d) and 1 cycle of MPA (5mg/d x 12 d at week 6 of E2 add-back). The rationale for the MPA is to prevent break-through bleeding, and thus enhance participant retention, and to prevent potential endometrial hyperplasia, although this is unlikely to occur during the 3-mo intervention. Additionally, we are interested in isolating the effects of E2 alone and not in combination with MPA because of the potential antagonizing effects of MPA on E2 action and because MPA has been shown to have negative effects on cognition. Thus, although technically a combination HT intervention, the add-back is E2-based, with minimal progesterone exposure. The first 6 months of drug intervention will be done as part of the FAME study, thus there will be no cost to this proposed sub-study during this period. Study drug for the 3-month E2 add-back portion unique to this sub-study will be paid for by the sub-study (Figure 3).

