**Pulse wave velocity.** Arterial stiffness will be measured using the combination of high-resolution ultrasonography and applanation tonometry in a large elastic artery in the central circulation (carotid). Indirect measures of central arterial stiffness (pulse-wave velocity [PWV], pulse wave analyses [PWA]) will be performed using the SphygmoCor XCEL (Atcor) system^89. PWV is measured using a blood pressure cuff placed on the upper thigh and applanation tonometry of the carotid artery in the neck. PWA provides a measurement of central aortic blood pressure and augmentation index by placing a blood pressure cuff over the brachial artery in the upper arm^89. The

brachial artery waveform is analyzed by the SphygmoCor to provide a central aortic waveform, and central blood pressure measurements and augmentation index. Although PWV is an indirect measure of arterial stiffness, it has been a gold standard in the literature, including studies of arterial stiffness and cognitive function.

***fMRI measurements.*** The scanning portion of the study will take place at the Intermountain Neuroimaging Consortium at the Center for Innovation and Creativity at [name]. The MRI device for these scans is FDA approved for research with human subjects and has all the safety inherent in a clinical MRI scanner. The radio frequency fields conform to guidelines determined by the FDA and the FDA has designated MRI scanners to be a non-significant risk device. MR techniques non-invasively produce images and measurements from tissues in the intact, living human.

Following the informed consent process, but prior to going into the MRI scanner, the MRI technologist on duty will ask participants to remove all jewelry and metal objects from their pockets. Participants will be required to change into scrubs to prevent any possible risk from metallic objects or decorations in their clothing.

In an MRI scan the subject lies down on a table and is placed into a long donut-shaped magnet. A specially designed coil will be placed around the head to provide better images (as is done with standard clinical examinations). As the MRI scan is performed, the subject will hear loud rapping and knocking noises that are normal for a MRI scan.

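### Pregnancy rules out an MRI scan, but the scan-day urine test depends on the woman being unsure, and the available text ties no routine pregnancy check to the follow-up scans

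*Combined protocol and SAP*

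**What the plan says.** Section 3.b (Methods, Subjects) makes pregnancy an exclusion by ruling out "any contraindication to magnetic resonance scanning (e.g., metal in body, claustrophobia, pregnant"), and says that candidates are screened for these exclusions before they take part in the MRI study. It names no method and does not say that the screen is repeated at later scans. Protection of Human Subjects, section 1.c, describes the MRI risk to pregnant women and fetuses as unknown.

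For the scan itself, section 2.b (Protections Against Risks, fMRI item) provides: "If they are unsure about whether or not they may be pregnant, female participants will be given the opportunity to complete a urine pregnancy test". The test is done just before scanning, and a positive result stops the scan.

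The routine check belongs to the injections. Under Drug intervention: "Absence of pregnancy will be confirmed before each dose". Section 2.b (Study drugs) repeats this and requires non-hormonal contraception.

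On scan times, section 3.b says: "Volunteers will undergo vascular and cognitive/fMRI testing at baseline and 6 months, corresponding to the beginning and end of the FAME study". Add-back women are scanned again at 9 months. The Sub-study paragraph adds "An additional group of up to 30 late-perimenopausal or postmenopausal women", who have one scan, receive no injections, and are excluded for MRI contraindications.

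**The concern.** A test that depends on doubt misses the woman it is most needed for, because someone with an unsuspected pregnancy is not unsure. Loss of periods is an expected effect of the study drug; the protocol notes that "participants on GnRHa may know their assignment because of the induction of amenorrhea and menopausal symptoms". A missed period on GnRHa therefore prompts little doubt, and section 2.b itself warns that loss of periods does not protect against pregnancy.

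Followed as written, the plan could allow a woman with an unsuspected early pregnancy to be scanned despite the protocol's own exclusion. The stake is participant safety and the enforceability of that exclusion. No estimate, power figure or analysis is affected.

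**Working it through.** The plan gives no figure to reproduce. The check compares the stated safeguards scan by scan, then works out the possible gap and the cost of a fix.

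**Safeguards at each scan**

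- *Baseline, randomised women.* FAME excludes pregnant women, MRI exclusions are screened, and testing falls on cycle days 2-6 (section 3.b). This is reasonable cover.
- *Month 6, placebo women.* They are not suppressed and keep the cue of a missed period. The cycle-day rule is stated for baseline only. Their routine check is the one before an injection.
- *Month 6, GnRHa women.* They are suppressed, so pregnancy is unlikely, but the menstrual cue is largely lost: Drug intervention cites amenorrhea in 61%, 86% and 90% of treated women with fibroids after 1, 2 and 3 months. Their routine check is again the one before an injection.
- *Month 9, add-back women.* The same applies, since GnRHa continues.
- *Sub-study, single scan.* The entry screen for MRI contraindications, which include pregnancy, comes before the scan. No test is named, and there is no injection-linked check.

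At every scan the conditional urine test is also available. The clinician review every 4 weeks covers medications, health status and study-drug concerns; no pregnancy test is named in it.

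**Time since the last routine check**

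Inputs: section 1.c (Study drugs) gives 6 monthly doses, and 9 in all with add-back. Exact days are not given in the available text.

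- If an injection is given at the scan visit, the gap is 0.
- If doses fall at months 0 to 5 and, with add-back, at months 6 to 8 (an assumption), the gap is 6 − 5 = 1 month for women who stop at six doses, and 9 − 8 = 1 month at the last add-back scan. That is about 4 weeks.
- Section 3.f says visits 2 and 3 take place while women are receiving GnRHa, which fits a scan inside a dosing interval and hence a value in between.

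The range is 0 to about 4 weeks, and the text does not narrow it.

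**Number of tests if the check became routine**

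Inputs: 51 randomised women, all assumed to be scanned at month 6. The add-back group is 10 under Drug intervention ("A subset (N=10) of women receiving GnRHa will continue for an additional 3 mo") and 17 in section 3.c, so both are carried. The sub-study has at most 30 women, and the late-perimenopausal share is not stated.

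- Follow-up scans: 51 + 10 = 61, or 51 + 17 = 68.
- Adding the sub-study, if all 30 needed a test: 61 + 30 = 91, or 68 + 30 = 98.
- Full range: 61 (add-back of 10, no late-perimenopausal women) to 98 (add-back of 17, all 30 late-perimenopausal).

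**The case against.** The strongest reply is that the protocol already layers its protection and that universal testing is a reviewer's preference. Pregnancy is excluded and screened for, absence of pregnancy is confirmed before each dose, contraception is mandatory, a clinician sees each woman every 4 weeks, and the scan-day test comes with a firm rule not to scan. The scanner adds little concern of its own: "the FDA has designated MRI scanners to be a non-significant risk device". The risk factors also tend not to coincide. Women who lose the menstrual cue are suppressed, and placebo women, who are not suppressed, keep the cue. All of this stands, and it is why the point is minor. None of these measures, however, verifies the exclusion on the day of the follow-up scan.

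A second reply is that the timing gap may not exist. Figure 2 (study design) and Figure 4 (timeline) are not visible in the available text, and the first six months of dosing follow the parent FAME protocol, which is not available here and may test at month 6. This also stands. It would be wrong to say that the plan has no visit calendar. Figure 3 lists no pregnancy test, but it also omits the required pre-dose checks, so its silence shows nothing.

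A third reply concerns the sub-study. A reader might infer that these women have no pregnancy safeguard. The documents do not support that: they are excluded for MRI contraindications, and with only one scan the entry screen must come before it. What remains is that no test is named for late-perimenopausal women.

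**Conclusion.** The point holds as an optional safety improvement. The protocol sets an exclusion, calls the risk unknown, and leaves the scan-day test to the woman's own doubt, which is a weak trigger when amenorrhea is an expected drug effect. Its routine checks are attached to doses, not scans.

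The size is small. The gap since the last check is somewhere between 0 and about 4 weeks. The number of exposed pregnancies cannot be derived and is likely zero or very small.

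A reader might go further and count unprotected scans. With doses assumed at months 0-5 and 6-8, each of the 51 women has no injection due at her last scan, giving 51 of 68 or 51 of 61 follow-up scans. The documents do not support that count. It rests on one assumed calendar, and it would be 0 if injections coincided with the scans. It also treats suppressed women and cycling placebo women as equally at risk. No such count should be reported.

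**What to change.** In section 2.b (fMRI item), replace the conditional offer with wording such as: *Every woman who could become pregnant will have a urine pregnancy test immediately before each follow-up scan (6 and 9 months), and late-perimenopausal women will have one before the single sub-study scan, unless a negative pre-dose or FAME pregnancy test was obtained at the same visit or within a few days before it. A woman whose test is positive will not be scanned.*

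Only the trigger changes; the test, its timing and the rule not to scan are already in the protocol. No extra baseline test is proposed, and Figure 3 need not change. If FAME already tests every woman close to the month-6 scan, citing that test would cover that scan, but not the 9-month or sub-study scans, which lie outside FAME.

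The cost is one sentence and at most about 61 to 98 urine tests, fewer wherever a recent negative test counts.
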